PROTOCOL TITLE: Assessment of a novel sensing catheter during automated insulin delivery in patients with Type 1 Diabetes

STUDY SITE: Oregon Health Science University
[name]
[name]

FUNDING: National Institutes of Health

PRINCIPAL INVESTIGATORS: [name] MD; [name] PhD

CO-INVESTIGATORS: [name] MBBS
[name] MD
[name] RN MSN ANP-BC, BC-ADM
[name] MD

Background:

Closed-loop systems are an emerging technology that automate hormone delivery. They are quickly paving the way to revolutionize the treatment of type 1 diabetes. Several categories have emerged: dual-hormone (insulin and glucagon) closed-loop systems and closed-loop systems with insulin only. Already, the benefit of improved glycemic control compared to current open-loop pump therapy has been demonstrated in several trials. Hovorka et al. recently showed that for people with T1D, glucose control could be improved when using a single-hormonal AP system for 12 weeks under free living conditions compared with sensor-augmented pump (SAP) therapy in a randomized multicenter cross-over trial [17]. Participants were in euglycemia for 11% more time using the AP system as compared to SAP therapy. Kropff et al. also recently published results from a long-term single-hormone study showing that when patients with T1D used an AP during evening hours and while sleeping, using SAP during the day, the time spent in euglycemia was increased compared with participants who used SAP 24-hours per day [18]. HbA1c dropped more significantly when using the AP (-0.3%) compared with SAP (-0.2%), though the improvement was modest.

The study described within this protocol is designed to test the efficacy of a single hormone closed-loop algorithm for managing blood glucose in type 1 diabetes using insulin only. In addition, this study will evaluate the feasibility of measuring glucose continuously in the immediate vicinity of subcutaneous insulin delivery. We hypothesize that with the use of the Pacific Diabetes Technologies continuous glucose monitoring and insulin infusion system, there will be no significant difference, in terms of sensing accuracy, between devices delivering insulin lis-pro and devices delivering saline control.

Primary Objectives:

- To assess the impact of lispro on glucose sensing as compared to a saline control.

Secondary Objectives:

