- To assess the glucose control achieved in adults with type 1 diabetes with the use of the OHSU closed-loop system.
- To assess the tolerability of the PDT glucose sensor.

Study Hypothesis:

We propose that the accuracy of the PDT glucose sensor is not impacted by the delivery of lispro insulin as compared to a saline placebo.

Endpoints**Primary Endpoints**

- Sensor accuracy as determined by mean absolute difference (MAD) for reference YSI venous blood glucose values ≤ 75 mg/dL and mean absolute relative difference for reference YSI venous blood glucose values >75 mg/dL

Secondary Endpoints (duration: entire study):

- Percent of time with sensed glucose between 70 – 180 mg/dl (based on Dexcom G5 CGM)
- Percent of time with sensed glucose <70 mg/dL (based on Dexcom G5 CGM)
- Percent of time with sensed glucose <54 mg/dl (based on Dexcom G5 CGM)
- Percent of time with sensed glucose >250 mg/dL (based on Dexcom G5 CGM)
- Mean sensed glucose (based on Dexcom G5 CGM)
- Number of carbohydrate treatments (defined as 15 or 20 grams of carbohydrate)
- Total amount of insulin delivered (in units/kg)

- Mean score on visual analog scale at 15 and 120 minutes after insertion, and at end of study
- Mean score on Draize scale at end of study

Study Type

This is a single center, one treatment trial designed to compare the sensor accuracy of the PDT sensing catheter when utilized to deliver lispro insulin as compared to a saline control.

Study Population

Study population will be adults with type 1 diabetes, ages 21 – 65 years of age. Younger subjects are excluded as it is appropriate to assess safety first in the adult population. 10 subjects will be recruited to participate in studies.

Power Analysis

Since data have not previously been obtained in humans (variance is unknown), this study is exploratory and not powered.

Protocol Summary:

[figure not shown]
Subjects will undergo one 12 hour inpatient study. During this intervention visit, subjects will wear two t:slim insulin pumps to deliver insulin or saline through two investigational PDT glucose sensing cannulas, and a Dexcom G5 CGM to measure glucose. The subject will come to

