After preparation of the skin with isopropyl alcohol followed by Chloraprep One-Step (2% chlorhexidine gluconate and 70% isopropyl alcohol), the two investigational PDT glucose sensing cannulas will be inserted subcutaneously in the abdomen, each at least 5 cm from the subject's insulin cannula and at least 5 cm from one another. For subjects allergic to Chloraprep, isopropyl alcohol will be used. The study investigator (PI or co-investigator, i.e. physician or nurse practitioner who has been trained in internal medicine) will manually insert each cannula into the subcutaneous tissue or will insert the cannula with the aid of a spring-operated insertion device. To ensure proper cannula insertion, a written manual and direct in-person training

(including troubleshooting) will be provided by Pacific Diabetes Technologies. The rigid stainless steel cannula will extend 12 mm into the tissue at a 35-45 degree angle (depth beneath skin surface, approximately 7-8 mm). After insertion, a small amount of saline (0.5 ml) will be delivered through each cannula to verify patency. In between usages, the insertion device will be thoroughly cleaned with SaniCloth AF-3 wipes.

The cannula is attached to a sensor housing unit which is affixed to the skin with acrylate-based adhesive tape. An Electronic Module which includes a telemetry unit is connected to the sensor housing. In between use on study subjects, the reusable telemetry unit will be thoroughly cleaned with SaniCloth AF-3 disinfecting wipes. After insertion, the subject will be instructed to avoid vigorous activity until the sensing cannula is removed at the end of the study. The subject will also be asked to keep the device dry. Sensor data (electrical current proportional to glucose level) will be stored within the body-worn electronic module at least once every minute. Sensor data from these investigational sensors will not be used to control the FMPD single hormone algorithm or insulin dosing at any time. The subject will not be able to view the sensor output. A visual analog scale and questionnaire will be given to assess tolerability and pain of the glucose sensing cannulas at 15 and 120 minutes after insertion and just before the glucose sensing cannulas are removed at the end of the study (see Appendix D).

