Subjects will eat breakfast and lunch at 11am and 3pm respectively. Meals will be announced to the controller. For each meal, food items will be self-selected from the hospital menu with subjects asked to pick meals of 80-150 grams of carbohydrates. The number of grams of carbohydrates will be entered in the controller. Trained study staff will be present to assist subjects with entering of all meal carbohydrate amounts into the APC controller. The APC will automatically calculate and deliver 80% (nominal) of his/her typical pre-meal insulin dose based on their insulin to carbohydrate ratio through the t:slim insulin pump.

The Fading Memory Proportional Derivative (FMPD) algorithm will determine the insulin delivery rates for the closed-loop studies. The FMPD algorithm determines insulin delivery rates based on proportional error, defined as the difference between the current glucose level and the target level, and the derivative error, defined as the rate of change of the glucose. Each of these

errors is calculated over a time interval. The “fading memory” designation refers to weighting recent errors more heavily than remote errors. This weighting provides an adaptive component to the algorithm. In simple terms, the insulin rate is increased for high or rising glucose levels. Gain factors determine the degree to which proportional or derivative errors lead to changes in insulin delivery rates. Positive proportional errors (glucose level above target) and positive derivative errors (rising glucose level) call for an increase in the insulin delivery rate. With regards to the glucose target, % of premeal insulin bolus: these are current nominal values that may be adjusted within the FDA approved minimum and maximum range for each adjustable parameter.

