
Stopping Rules

The subject may withdraw at will at any time or at the discretion of the Investigator.

A subject must be withdrawn if any of the following applies:

1. Hypoglycemia: After initial stabilization, one episode of severe hypoglycemia (requiring the assistance of another person) or one episode of venous blood glucose < 50 mg/dl.
2. Hyperglycemia: After initial stabilization, venous blood glucose > 400 mg/dl for over 30 minutes.
3. Ketoacidosis: Venous blood glucose > 250 mg/dl accompanied by serum ketone level > 1.5 mM.
4. Protocol deviation having influence on efficacy or safety data as judged by the Investigator.
5. Substantial and repeated non-compliance with trial procedures
6. Pregnancy
7. Intention of becoming pregnant

The study may be stopped if the glucose sensing cannulas have repeated inability to acquire sensor data, such as telemetry issues.

Data Analysis

Note that it was not possible to carry out a formal sample size power analysis for this feasibility study since data have not previously been obtained in humans (variance is unknown). However, we expect the sample size proposed here (10) is adequate to detect a difference between the insulin formulation and saline, based on our earlier studies in swine. The data obtained in this study will be used to calculate variance so that formal power analyses can be used for subsequent, more formal, studies.

This study design will allow a comparison of sensing accuracy after insulin vs after saline administration through the sensing cannula. For example, this study design will allow assessment of the magnitude of artifact, if any, from the insulin preservatives, as was noted in pig studies with the non-redox mediator sensor. It will also assess the potential for underestimation of glucose due to uptake into fat as a result of local insulin delivery [19], [20].

For each subject, we plan to acquire data from the PDT sensor which is represented by an

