electrical current in nanoamperes (nA). We will match these sensor values with YSI values which are in units of mg/dL. We will then do a linear least squares regression between the YSI glucose and the sensor current to create an equation that estimates the actual glucose from the sensor current. This equation will have the form of $y=mx + b$, whereby y is the estimated glucose (mg/dL), m is the slope (mg/dL/nA), x is the current measured by the sensor (nA), and b is the intercept or background current (nA). The slope and intercept will be estimated for each patient and for both the saline sensing catheters and the insulin sensing catheters. We will then do a t-test between the slopes and the intercepts comparing these values between the saline sensing catheters and the insulin sensing catheters. The hypothesis is that the null hypothesis (the mean value of both the slope and intercept values are identical between the saline and insulin sensing catheters) is true which will be estimated by a p-value being greater than 0.05.

Another key end point will be glucose sensor accuracy (absolute difference, relative difference, and absolute relative difference) during insulin vs during saline delivery. These metrics will be calculated by using two types of calibration schemes: a one-point calibration with fixed offset, performed prospectively before meal administration, as described earlier [21]; and a retrospective all point calibration as proposed for early device evaluation, as proposed by Heinemann and Ludwig [22]. In addition to mean and median absolute difference, mean and median relative difference, and mean and median absolute relative difference, other accuracy metrics will include signed difference (bias). Error grid analyses will include Clarke, Parkes and continuous analyses. Bland-Altman analysis will be used to stratify accuracy as a function of glucose level.

In addition to the glucose sensing data described above, the subjects enrolled in the proposed clinical study will be asked to provide tolerability scores, which will include visual analog scales, to assess their level of comfort. During the study, skin irritation (Draize scores) will also be recorded. The tolerability and Draize scores will provide key data that will be used to support subsequent device modifications that reduce discomfort and skin irritation.

Confidentiality and Protection of Human Subjects

RISKS and BENEFITS

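### No post-bolus window is defined for sensor accuracy; if a lispro artifact is assumed to last 30–90 min per meal bolus, session means dilute it about 3- to 9-fold

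*Combined protocol and SAP*

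**What the plan says.** The primary objective is broad: "To assess the impact of lispro on glucose sensing as compared to a saline control". The Data Analysis section narrows it. It says "This study design will allow a comparison of sensing accuracy after insulin vs after saline administration through the sensing cannula", and names two effects of interest: "assessment of the magnitude of artifact, if any, from the insulin preservatives, as was noted in pig studies" (seen there with a different sensor type), and "It will also assess the potential for underestimation of glucose due to uptake into fat as a result of local insulin delivery".

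The metrics that follow carry no time anchor. The primary endpoint is "Sensor accuracy as determined by mean absolute difference (MAD) for reference YSI venous blood glucose values" at or below 75 mg/dL, with the relative version above 75 mg/dL. It is split by glucose level and not by time. The Data Analysis section adds "Another key end point will be glucose sensor accuracy (absolute difference, relative difference, and absolute relative difference) during insulin vs during saline delivery", under two calibrations: a prospective one-point calibration done before a meal, and a retrospective all-point calibration. It also plans signed bias, three error-grid analyses, and a Bland-Altman analysis stratified by glucose level. A separate t-test compares one fitted slope and one intercept per catheter.

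The exposure does have a time structure. Under 12 hour Treatment Visit: "Subjects will eat breakfast and lunch at 11am and 3pm respectively. Meals will be announced to the controller". Each announced meal of 80–150 g carbohydrate triggers an automatic bolus, and the saline pump runs at the same rates as the insulin pump. Reference glucose is drawn every 15 minutes. For the investigational sensors, "Sensor data (electrical current proportional to glucose level) will be stored within the body-worn electronic module at least once every minute".

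**The concern.** An effect of insulin or its preservatives at the catheter tip would plausibly be largest shortly after a large local dose. The design delivers two such doses at known times, with a matched saline dose in the same subject. An analysis that pools all reference pairs from a catheter gives the post-bolus pairs no more weight than the rest, so a real error confined to those periods appears as a small change in the session mean. The study hypothesis is that lispro does not affect accuracy, so lost sensitivity works in favour of that hypothesis. A report of similar session accuracy could then be read as showing no artifact after a bolus, a period that the planned summaries do not examine separately.

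**Working it through.** **Reproducing the plan's figures.** The sample size of 10 has no stated SD, effect size or power, so there is nothing to reproduce. The sampling schedule can be checked. With closed loop from 9:30 (12 hour Treatment Visit) to about 18:00, the session is 510 min and gives 510/15 + 1 = 35 samples, or 35 × 0.5 mL = 17.5 mL. From 9:00 (arrival at 7:00 plus the 2 h warm-up) it is 540 min, 37 samples and 18.5 mL. The protocol states about 18–20 mL per study. One sample per 15 min over 8.5–9 h is therefore a fair reading.

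**Dilution of a mean metric.** With two boluses and an artifact of d minutes after each, fold dilution = session minutes / (2d). The duration d is an assumption.

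| d (min per bolus) | 510 min session | 540 min session | 420 min (scored 11:00–18:00, after pre-meal calibration) |
|---|---|---|---|
| 30 | 8.5 | 9.0 | 7.0 |
| 60 | 4.3 | 4.5 | 3.5 |
| 90 | 2.8 | 3.0 | 2.3 |

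**The same in MARD units.** Assume a relative error SD of 12% and an artifact of +20%. Neither figure is in the documents. Mean absolute error is 12 × √(2/π) = 9.6% without the artifact. With it, the folded-normal mean is 12 × √(2/π) × exp(−20²/(2 × 12²)) + 20 × [1 − 2Φ(−20/12)] = 2.4 + 18.1 = 20.5%. If m of 35 pairs are affected, session MARD = [20.5m + 9.6(35 − m)]/35:

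- 30 min, m = 4: 10.8%
- 60 min, m = 8: 12.1%
- 90 min, m = 12: 13.3%

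The excess of 10.9 points inside the window becomes 1.2, 2.5 and 3.7 points over the session.

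**Effect of the all-point calibration.** The regression described in the Data Analysis section predicts glucose from current with an intercept, per subject and per catheter. Suppose the retrospective all-point calibration is such a fit and is scored on the same pairs. The normal equation for the intercept is Σ(estimated − YSI) = 0. Mean signed difference in mg/dL is then exactly zero for the lispro and the saline catheter alike, whatever the artifact. The signed relative difference is not forced to exactly zero.

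The intercept alone already redistributes an artifact. For a constant shift A on 8 of 35 pairs, removing the overall mean leaves (27/35)A = 0.77A inside the window and −(8/35)A = −0.23A outside it; 8 × 27/35 and 27 × 8/35 cancel. A fitted slope can absorb more, because post-meal glucose tends to be high.

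A simulation illustrates this (assumed meal peaks of +100 mg/dL, SD 12%, artifact +20%, all-point least-squares fit). Session MARD, saline against lispro, was 8.6 v 9.3 at 30 min, 8.6 v 9.2 at 60 min and 8.6 v 8.7 at 90 min. With +60 mg/dL peaks and 90 min, lispro looked better (7.5 v 7.0). Over these cases the lispro-minus-saline signed bias inside the window was +8 to +23 mg/dL. The size and even the sign of the session difference depend on the assumed glucose curve; the windowed bias stayed clearly positive.

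**Slope and intercept test.** With an assumed +30% artifact, a simulated fitted slope moved by −0.17 to −0.29. That test is not diluted in the way a mean is, so the table does not apply to it.

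**The case against.** The strongest reply is that whole-session averaging is inferred from silence. The entire-study duration is attached to the secondary endpoints, not the primary, and the one-point calibration before a meal may shorten the scored period. That stands, and is why the 420 min column is shown; it lowers the range but does not supply a window.

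A second reply is that dilution need not mean non-detection. Under the SD 12%, +20% model, without the all-point fit, a paired t-test of session MARD in 10 subjects has power of about 50%, 96% and over 99% for 30, 60 and 90 min. An assumed between-sensor SD of 2 MARD points lowers this to 18%, 55% and 87%. So it cannot be said that a clear artifact would vanish. It can be said that detection would depend on quantities that the plan does not know.

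Third, signed bias and error grids are already planned, and the trial is exploratory and unpowered, with minute-level data retained. Error grids can show individual outlying pairs, but not whether they cluster after a bolus. A later time-course analysis is possible, but its windows would then be chosen with the data in view.

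A reader might also infer more than the documents support:

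- **That most lispro arrives in the two meal boluses.** No carbohydrate ratio or basal rate is given. Assumed ratios of 5–20 g/U and background rates of 0.5–2.0 U/h give a meal share of 27–92%.
- **That the artifact could slip between reference samples.** This needs a duration under 15 min, where dilution is at least 510/30 = 17-fold. It is a different scenario from 3- to 9-fold: a 30 min artifact always meets two samples per bolus.
- **That the trial exists to find a transient artifact.** The objective is any lispro effect, and no text describes the artifact as transient.

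**Conclusion.** The point holds as a gap in the accuracy analysis. The plan names effects to be assessed after insulin, delivers insulin boluses at two known times, and defines no window around them. The dilution of about 3- to 9-fold rests on an assumed artifact of 30–90 min per bolus and on scoring over 510–540 min; it is about 2.3- to 7-fold over 420 min. The zero session bias is exact, but only if the all-point calibration is a least-squares fit with an intercept, scored on the same pairs.

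A reader might conclude that dilution drives the plan's rule of reading p > 0.05 as support for no difference. It does not: that rule is attached only to the slope and intercept comparison, and no such rule is attached to MAD or MARD. For an exploratory study of 10 subjects this is a worthwhile, cheap improvement and not a flaw that invalidates the trial.

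**What to change.** Add to the Data Analysis section:

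1. **Windowed accuracy.** For each subject, report the paired lispro-minus-saline difference in signed bias and in absolute (relative) error for YSI pairs 0–30, 30–60 and 60–120 min after each meal bolus, and for all other pairs. Separate windows are needed because a single 120 min window would hold 2 × 120/15 = 16 of 35 pairs and still dilute a 30 min artifact 4-fold.
2. **Calibration.** Use the pre-meal one-point calibration as the main version, because an all-point fit can absorb the artifact. Report the all-point version alongside.
3. **Time course.** As supporting description, plot and summarise the one-minute lispro-minus-saline difference around each bolus in calibrated glucose units with the offset removed. Raw current scaled to its pre-bolus mean is not suitable. If glucose doubles, a sensor with no background current reads 2.0 times its baseline and one with 20% background reads 1.8 times, a difference without any lispro effect.
4. **Conclusion.** State any finding of no impact for the post-bolus windows as well as for the session.

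No new data are needed. The cost is some extra descriptive tables and few pairs: about 4, 4 and 8 per catheter per subject in the three windows, against 35 − 16 = 19 elsewhere. The windowed results should therefore be presented as estimates with intervals.

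### If the all-point calibration is the YSI-on-current regression, signed error by glucose level carries a built-in trend that grows with sensor noise, so a merely noisier lispro catheter could be misread as level-specific underestimation

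*Combined protocol and SAP*

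**What the plan says.** Data Analysis describes the following fit: "linear least squares regression between the YSI glucose and the sensor current to create an equation that estimates the actual glucose from the sensor current". Estimated glucose is the response and current the predictor. The fit is made catheter by catheter: "The slope and intercept will be estimated for each patient and for both the saline sensing catheters and the insulin sensing catheters". Slopes and intercepts are then compared between saline and insulin catheters by t-test.

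Accuracy is computed under two schemes. One is "a one-point calibration with fixed offset, performed prospectively before meal administration"; the other is a retrospective all-point calibration, defined by a citation and not by a formula. The metrics include signed difference, and "Bland-Altman analysis will be used to stratify accuracy as a function of glucose level". The plan does not say whether level means YSI, the sensor estimate or the mean of the two.

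The primary endpoint (Endpoints) is banded by the reference value: "mean absolute difference (MAD) for reference YSI venous blood glucose values ≤ 75 mg/dL", with the relative metric above that cut. Data Analysis also names a directional effect of interest: "It will also assess the potential for underestimation of glucose due to uptake into fat as a result of local insulin delivery".

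**The concern.** Fitted values from a regression of YSI on current are pulled towards the session mean. A sensor that is right on average at every glucose level, but noisy, will after this calibration read high when YSI is low and low when YSI is high. Each catheter has its own line, so the catheter with the lower R² shows the steeper false trend.

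The study looks for underestimation caused by local insulin. If the lispro catheter were only noisier, the all-point results would show it under-reading saline at high glucose and over-reading it at low glucose. Extra noise is a real loss of accuracy, but it is a different finding from local uptake. Nothing in the plan separates the two.

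**Working it through.** **Inputs from the documents.** 10 subjects, each wearing both catheters. Sampling every 15 minutes from a 9:30 start to 6 pm (12 hour Treatment Visit) gives 8.5 × 4 + 1 = 35 pairs per catheter. The plan states that the variance is unknown and gives no power, margin or SD, so it has no figure to reproduce.

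**Assumptions.** YSI mean 150 and SD 50 mg/dL (range 35 to 65 for the SD). Sensor noise SD in glucose-equivalent mg/dL: 10 to 20 for saline, 20 to 40 for lispro. The scatter lies in the current, with YSI as reference.

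**Algebra.** Let d = estimate - YSI and V = variance of YSI within one fit. For a least-squares fit, var(estimate) = R²V and cov(estimate, YSI) = R²V.
- Slope of d on YSI: (R²V - V)/V = -(1-R²).
- Slope of d on the two-method mean: [(R²-1)V/2] / [V(1+3R²)/4] = -2(1-R²)/(1+3R²).
- Slope of d on the estimate: 0.

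These are identities; only the value of R² is assumed.

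| R² | slope on YSI | slope on two-method mean |
|---|---|---|
| 0.9 | -0.10 | -0.2/3.7 = -0.054 |
| 0.8 | -0.20 | -0.4/3.4 = -0.118 |
| 0.7 | -0.30 | -0.6/3.1 = -0.194 |

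**Size of the bias.** With independent draws, noise SD 25 gives R² = 2500/(2500+625) = 0.8. Simulated bias at YSI ≤75 is then about +17.5 mg/dL. With autocorrelated glucose (AR(1) 0.9 per 15 minutes) and the same noise it is about +14. With noise SD 20 and autocorrelated glucose it is about +10 to +11. At YSI 180 to 250 the corresponding range is about -7 to -11. Autocorrelation shrinks the bias because sessions that contain low values also tend to have low session means.

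**Lispro against saline, no true effect of lispro on level.** 2000 simulated trials, autocorrelated glucose, noise SD 10 saline and 20 lispro:

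| | Saline | Lispro |
|---|---|---|
| R² | 0.91 | 0.73 |
| Bias at YSI ≤75 (mg/dL) | +3.6 | +11.0 |
| Bias at 180 to 250 | -2.2 | -7.2 |
| Bias above 250 | -2.8 | -10.1 |
| Slope of d on YSI | -0.09 | -0.27 |

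A paired t-test on the per-subject level slopes (two-sided 0.05) rejects in about 100% of trials on the YSI axis and 99% on the two-method mean. Over the whole assumed range, with lispro noise twice saline noise, rejection is 97 to 100%, and lispro bias runs from +9.5 to +27 at ≤75 and from -5 to -19 at 180 to 250. With equal noise (10 and 10) rejection is about 4%, so unequal noise drives the false contrast.

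**Alternatives, same data.** With current regressed on YSI and the line inverted, the false contrast is flagged in about 5% of trials and bias by YSI level is about 0 in both catheters. Under the one-point scheme it is also about 5%, with a median level slope of about 0 but larger errors.

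**Slope and intercept tests.** The expected fitted slope is the true slope times R². With a true slope of 10 mg/dL/nA, 10 × 0.91 = 9.1 and 10 × 0.73 = 7.3. The simulated means are 9.1 and 7.4, with intercepts -6 and +22. Both t-tests reject in over 99% of trials although the true lines are identical.

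**MAD at YSI ≤75.** Independent draws at R² 0.8 give 21.5 mg/dL with the planned fit and 18.8 inverted. With AR(1) 0.9 and noise SD 25 the values are 19.2 and 19.2.

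**The case against.** The strongest reply is that the plan does not rely on this regression alone. The one-point fixed-offset scheme has no systematic level slope, so a false trend in the all-point results would not be reproduced there. That stands, and a reader who takes the regression to be the plan's only route from current to glucose would be wrong. But the one-point scheme is noisier, and the plan does not say that the two schemes must agree.

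Two conditions are also unproved. The all-point scheme is defined by a citation and is not expressly equated with the regression. The level axis is undefined, and against the sensor estimate the trend is zero. Both stand as conditions, although the regression is the only all-point fit described and the primary endpoint bands by YSI. Nor is any test or decision rule planned for level-specific bias, in a study that Power Analysis calls exploratory.

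Three further readings are tempting and should be resisted:
- That the low-glucose MAD is inflated. This depends on the simulation design and disappears with autocorrelated glucose.
- That the artefact coincides with peak lispro delivery. Meals are announced and the controller doses from the entered carbohydrate (12 hour Treatment Visit), so the bolus is tied to the announcement and not to the later glucose peak.
- That the slope and intercept tests escape. They do not, and they are the only hypothesis tests that Data Analysis specifies.

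**Conclusion.** The point holds, conditionally. If the all-point calibration is the YSI-on-current fit, and level is YSI or the two-method mean, signed error by level has a built-in negative trend, steeper for the noisier catheter. Extra noise on lispro alone could then be misread as level-specific underestimation from local insulin. The existence of the trend is algebra. Its size, about +10 to +18 mg/dL at YSI ≤75 and about -7 to -11 at 180 to 250, rests on the assumed mean, SD, noise and autocorrelation; the 97 to 100% rejection rates rest on a twofold noise ratio. The slope and intercept t-tests are exposed to the same attenuation. The documents do not support saying that the primary MAD at ≤75 is overstated, or that the study must report a false effect. For an exploratory study of 10 subjects this is a change that should be made, not one that invalidates the design.

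**What to change.** - State whether the retrospective all-point calibration is the YSI-on-current regression.
- For signed bias by glucose level and for Bland-Altman, fit current on YSI for each catheter, invert the line, and plot and stratify the difference against YSI. Both parts are needed: against the two-method mean, the inverted fit shows the opposite trend, +2(1-R²)/(1+3R²), or +0.118 at R² 0.8.
- Compare slopes and intercepts from that same current-on-YSI fit. Noise in the current does not attenuate it, and its intercept is in nA, the unit that the plan assigns to the background current.
- Report R² or residual SD per catheter, so that a difference in noise is visible as such.
- Call a level-specific lispro effect only if the one-point results show it too.
- Use one calibration line for both halves of the primary endpoint (MAD at ≤75 and MARD above 75). The results above give no reason to move that endpoint off the planned line.

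The cost is a few lines of code and a short addition to Data Analysis, on data already to be collected. The drawback is a larger overall RMSE for the inverted fit, by a factor 1/√R²: 1/√0.8 = 1.12 (about 12%) and 1/√0.7 = 1.20 (about 20%). The penalty is greater for the noisier catheter.
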